## **Background and Introduction**

---

Chronic cough patients are treated for the etiologies of gastroesophageal reflux disease (GERD), cough variant asthma (CVA), upper airway cough syndrome (UACS) formerly called postnasal drip syndrome with varying benefit (4). Despite prolonged therapies with agents directed at GERD, UACS and CVA, these patients continue to experience persisting cough that is termed as idiopathic cough or unexplained cough. Studies have shown that cough can be unexplained or idiopathic in up to 42% of patients (5).

Obstructive sleep apnea (OSA) is a highly prevalent condition in the general population (6). A large retrospective study performed at Utah Valley Pulmonary Clinic identified a 44% prevalence of OSA in chronic cough population. 93% of patients treated with CPAP showed improvement in cough (2). Besides this study, a number of case reports have identified OSA as a perpetuating cause for chronic cough (7-8). Based on this, a number of mechanistic pathways by which OSA can lead to or perpetuate chronic cough have been identified (3).

Despite above reports, no study has conclusively shown that CPAP therapy alone provides improvement in cough relief as patients with chronic cough are often rendered multiple different therapies for GERD, CVA and UACS. Additionally no study till date has used a placebo arm to demonstrate improvement in cough intensity measurements with CPAP therapy.

The current study purports aims to establish a definitive relationship using a CPAP vs. sham CPAP arm to assess changes in subjective and objective cough measures in chronic cough patients with comorbid OSA. Sham CPAP therapy is a well-established modality to demonstrate efficacy of OSA therapy on a multitude of disease states, ranging from metabolic syndrome to reflux disease (9).

## **Purpose and Objectives**

---

**AIM:** To demonstrate that therapy of concomitant OSA in patients with chronic cough improves or resolves chronic cough.

Chronic cough is an important clinical problem in primary care and subspecialty practice (1). Besides the distress experienced by patients with chronic cough, significant healthcare resources are expended to understand the role of gastroesophageal reflux, asthma and post-nasal drip in understanding their contribution to cough.

Recently obstructive sleep apnea (OSA) has been found to be common in patients with chronic cough (2). More importantly, treatment of OSA with continuous positive airway pressure (CPAP) led to improvement in cough in chronic cough patients (2). Mechanisms by which

OSA therapy with CPAP can improve cough includes beneficial effects on reflux and airway inflammation (3).

Our study purports to definitively establish that CPAP therapy for treatment of OSA in chronic cough patients improves cough. While these patients with chronic cough are not routinely screened and treated for OSA, our study aims to evaluate these chronic cough patients with screening questionnaires for OSA and if necessary with polysomnography and randomize them to either CPAP or sham CPAP for 6 weeks. During this 6 weeks patients will undergo assessments for cough using the following

- Validated cough questionnaires
- Objective cough monitoring using cough monitors provided by [name] in UK
- Measures of airway inflammation using exhaled breath condensate.

## **Study Population**

---

**Age of Participants:** 18-70

**Sample Size:**

At Utah: 58 subjects  
All Centers:

**Inclusion Criteria:**

Patients will be recruited from outpatient pulmonary clinics that meet the following criteria:

1. Cough of more than 2 month duration
2. Age more than 18 years
3. Smoking < 5pk-years with history of tobacco use more than 10 years prior.
4. Evaluation and treatment by other providers for suspected GERD, UACS or CVA for at least 1 month
5. Normal chest radiography or CT scans (patients with upto 2 lung nodules less than 3 mm to be allowed if there is no history of malignancy elsewhere).
6. Normal spirometry with predicted DLCO more than 50% predicted. PFT criteria: No evidence of airflow limitation (FEV1/FVC >0.7) or significant chest restriction (FVC>70% predicted) with predicted DLCO more than 50% predicted.
7. STOP-BANG score of 3 or more requiring OSA evaluation

**Exclusion Criteria:**

Exclusion criteria

1. Pregnancy
2. Positive methacholine challenge test (if it is performed).

3. Prior history of asthma for which inhaled or systemic corticosteroids have been used.  
Patients with wheezing on auscultation will also be excluded.
4. Recent pneumonia (less than 6 months)
5. Congestive heart failure, acute or chronic renal disease, jaundice or decompensated chronic liver disease, pulmonary embolism, stroke or neurodegenerative disease, malignancy
6. Age more than 70 years
8. Use of supplemental oxygen or PAP therapy (if patients have been diagnosed with OSA in past but were non-compliant with PAP therapy, they will not be excluded)
7. Use of opiates, benzodiazepines (cough suppressant solutions containing codeine derivatives not excluded)
8. Alcoholism, drug dependence (including chewing tobacco) or illicit drug use
9. Prior Nissen fundoplication, esophageal or laryngeal surgery.
10. Craniofacial abnormalities that preclude CPAP placement.

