## **CLINICAL PROCEDURES:**

We anticipate these will already be performed as part of **clinical evaluation prior to enrollment in the study (this is done as part of routine evaluation for chronic cough)**.

- Chest radiography
- Pulmonary function testing (spirometry, single breath diffusion capacity measurement)
- Exhaled nitric oxide testing if available
- STOP-BANG screening questionnaire
- Full-night attended or unattended polysomnography if STOP-BANG questionnaire abnormal with clinical suspicion for sleep-disordered breathing.

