### PRIMARY END-POINT

1. Change in LCQ score in CPAP-treated patients vs. sham CPAP-treated patients. This will be compared between baseline LCQ score prior to initiation of CPAP or sham CPAP and compared to the LCQ score at 6 weeks.
2. Change in Leicester cough monitoring measured at baseline and at 6 weeks after CPAP or sham-CPAP therapy.
3. Change in measurements of exhaled breath condensate 8 isoprostane, IL-6, nitrite/nitrate, H2O2 and LTB4 at baseline and at 6 weeks.

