## NUMBER OF SUBJECTS TO BE ENROLLED

Based on the results of a recently concluded CPAP intervention study for chronic cough, mean change in LCQ with CPAP was + 4.1 (with 4.14 SD in baseline and followup LCQ scores)

Mean change in LCO with placebo was 1.1 (Lancet 2012)

Expected difference between mean LCOs of two groups 3.0

- To achieve 80% difference to detect a significant difference of 0.05 level for a difference means of 2.58, 19 subjects per group needed assuming no attrition using a mixed models analysis of repeated measures data.

- Assuming 33% attrition rate due to CPAP noncompliance, 29 subjects per group needed.

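### Eligibility does not address current ACE-inhibitor use and does not protect the baseline cough measures from a recent acute respiratory infection; the cost is some power and a less interpretable null result, not bias

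*Combined protocol and SAP*

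**What the plan says.** The Inclusion Criteria ask for long-standing cough ("Cough of more than 2 month duration"), little smoking history, normal imaging and near-normal lung function. They also require prior work-up of three named causes: "Evaluation and treatment by other providers for suspected GERD, UACS or CVA for at least 1 month".

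The Exclusion Criteria add steroid-treated asthma, wheezing, heart failure, malignancy, and laryngeal or esophageal surgery. The only infection listed is pneumonia: "Recent pneumonia (less than 6 months". The one criterion on prescribed sedatives and analgesics reads "Use of opiates, benzodiazepines (cough suppressant solutions containing codeine derivatives not excluded". ACE inhibitors are not named.

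The section Clinical Procedures lists chest radiography, lung function, exhaled nitric oxide, STOP-BANG and polysomnography, and says that "this is done as part of routine evaluation for chronic cough". It lists no medication review and no infection-free period.

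The first primary end-point is "Change in LCQ score in CPAP-treated patients vs. sham CPAP-treated patients", from baseline to 6 weeks. Changes in 24-hour cough monitoring and in breath-condensate markers over the same interval are also listed as primary. Under Statistical Analyses, each patient serves as his or her own control. The section on number of subjects states "19 subjects per group needed assuming no attrition using a mixed models analysis of repeated measures data", raised to 29 per group for 33% attrition.

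**The concern.** The Background says earlier work was inconclusive because patients were receiving several other therapies, and the criteria are plainly meant to isolate cough that OSA could be sustaining. Two gaps work against that.

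- **ACE inhibitors.** Drug-induced cough lies outside the mechanisms the protocol proposes for CPAP (reflux and airway inflammation). Such a patient may add little to the CPAP-sham difference. If the drug happens to be changed during the six weeks, the cough may clear in either arm.
- **Acute infection at Visit 1.** A patient with long-standing cough and a fresh infection remains eligible. The LCQ, a single 24-hour recording and the inflammatory markers would then be unrepresentative and would recover in either arm. Because the outcome is change from baseline, that recovery enters it directly.

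The first gap shrinks the expected difference; the second adds variance. Both lower power, and a null result would be harder to attribute to absence of a CPAP effect. Neither factor is planned as a stratifier or covariate.

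**Working it through.** **Inputs from the section on number of subjects.** Difference used for sizing 2.58 LCQ points; expected difference 4.1 − 1.1 = 3.0; SD 4.14 for baseline and follow-up scores; 80% power; "significant difference of 0.05 level" (sidedness not stated, two-sided assumed); 19 per group, 29 after 33% attrition.

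**Reproducing the plan's figures.**
- Attrition: 19 / (1 − 0.33) = 28.4, rounded up to 29; and 29 × 0.67 = 19.4. About 19 evaluable per arm is right.
- The 19 does not follow from the stated inputs alone. A two-sided two-sample t-test with SD 4.14 needs 41.4 per group for 2.58 and 30.9 for 3.0. Reaching 19 at 2.58 needs an unstated within-patient correlation of about 0.78 (change score) or 0.74 (baseline-adjusted). So 19 cannot be verified, but it is not shown to be wrong. I take the plan's power statement as given.

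**Effective SD.** With 19 per arm, two-sided 0.05 and 80% power, the t-test needs a standardised difference of 0.934. Hence SD = 2.58 / 0.934 = 2.76.

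**Dilution (ACE-inhibitor limb).** Let f be the share of patients who cannot respond at all. The expected difference becomes (1 − f) × difference. The values of f are assumptions.

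| f | From 2.58: difference | Power | From 3.0: difference | Power |
|---|---|---|---|---|
| 0% | 2.58 | 80% | 3.00 | 90% |
| 5% | 2.45 | 76% | 2.85 | 87% |
| 10% | 2.32 | 71% | 2.70 | 83% |
| 20% | 2.06 | 61% | 2.40 | 74% |

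From 3.0, power stays at or above 80% until f = 1 − 2.58/3.0 = 14%. Both columns use SD 2.76. If the 19 had really been derived for 3.0, the implied SD would be 3.0 / 0.934 = 3.21, and the 2.58 power column would apply to 3.0 as well.

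Mixing responders and non-responders in the CPAP arm also adds variance. A normal-approximation check from 2.58 that includes it (SD 2.84) gives 75%, 70% and 58% at 5%, 10% and 20%.

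**Noise (infection limb).** Assume 10% of baselines are depressed by 3 LCQ points and recover fully in either arm. Variance = 2.76² + 0.10 × 0.90 × 3² = 7.63 + 0.81 = 8.44, so SD = 2.90. Power is 76% from 2.58 or 87% from 3.0. The 10% and the 3 points are both assumptions.

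**The case against.** The strongest reply is that this is breadth of eligibility, a design choice, with a harm that cannot be sized from the documents. Several parts of that reply stand.

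- **Bias.** A reader might infer that these patients distort the comparison in favour of one arm. They do not: both factors are balanced in expectation by randomisation. Only chance imbalance in small arms remains.
- **No reserve.** A reader might infer that the 80% power has no margin. The plan expects 3.0 points and sizes for 2.58, which is 14% lower. The documents do not say whether that is a deliberate margin or a slip, so neither claim is established.
- **Infection as a cause that CPAP cannot treat.** With more than 2 months of cough and at least 1 month of work-up, an acute infection is hardly the qualifying cause. The patient still has the underlying cough, so this limb adds temporary noise rather than diluting the effect. A rule applied before baseline also does nothing about infection at 6 weeks.
- **Frequency and complete non-response.** No passage gives the share of ACE-inhibitor users or of infected baselines. All patients have OSA, and the Background says OSA may perpetuate cough, so a patient with two causes could respond in part. Complete non-response is the worst case.
- **Double counting.** If the earlier CPAP study behind the 4.1-point change enrolled such patients, some dilution is already in the planning figures. The documents do not say.

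None of this closes the gap. The plan already excludes by medication and by cause of cough, and no passage covers these two factors.

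**Conclusion.** The point holds as a moderate, inexpensive improvement. As written, the plan admits patients whose cough may lie outside its hypothesis and allows baseline measures to be taken during an acute infection.

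The harm is lost precision and an ambiguous null result, not systematic error. Under assumed shares of 5% to 20% complete non-responders, power falls to between 76% and 61% from 2.58, or between 87% and 74% from 3.0. These figures rest on the back-solved SD of 2.76, a two-sided 0.05 test and 19 evaluable per arm. They are illustrations, not estimates, and the true loss could be smaller for the reasons given above.

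The ACE-inhibitor gap is the main point; the infection gap is secondary. The documents do not support saying that either factor is common in this population, or that the trial is underpowered because of them.

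**What to change.** 1. Add to the Exclusion Criteria current ACE-inhibitor use, or use within a window before Visit 1 whose length the investigators set. Check it at the medication review that the opiate and benzodiazepine exclusion already implies. This is an eligibility rule only; it asks no one to start or stop a drug.
2. As a lesser change, defer the Visit 1 baseline measures when an acute respiratory infection is present or recent (window set by the investigators), with re-screening allowed.
3. Record both factors at baseline and at 6 weeks, so that changes and infections arising during follow-up can be described when the result is interpreted.

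**Cost.** A few lines in the protocol and screening form. ACE-inhibitor users are lost to a 58-patient study, and the loss grows with their share: if 20% of candidates were affected, about 20% would be turned away, and re-screening would not recover them. Patients with infection are mostly delayed rather than lost. If the sponsor judges the recruitment loss too high, item 3 alone would help interpretation but would not restore power. Eligibility should be settled before enrolment, because case mix cannot be repaired afterwards.

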## Design

---

Prospective Clinical Research  
Double Blind  
Randomized

Use of a Sham CPAP machine

## Study Procedures

---

### **Recruitment/Participant Identification Process:**

Participants will be recruited from pulmonary clinics, ENT clinics, primary care clinics, sleep clinics within the University of Utah healthcare system. Patients will be consented at either Clinic 3, pulmonary clinic or at the University of Utah Sleep Center.

Posters with information about the study will be hung in the clinic workrooms where they can be seen by clinic personnel but not by patients.

### **Informed Consent:**

#### **Description of location(s) where consent will be obtained:**

Clinic 3 (Pulmonary) at University of Utah Hospital Sleep-Wake Center, University of Utah

#### **Description of the consent process(es), including the timing of consent:**

Once patients meet study criteria based on results of STOP-BANG questionnaire and polysomnography, they will be eligible to be consented by the investigators.

### **Procedures:**

Patients with chronic cough that meet criteria for study inclusion will undergo screening and evaluation for OSA. This will be part of routine care. OSA is an important clinical problem that needs to be treated for impact on cardiovascular, metabolic and behavioral outcomes. It is anticipated that patients will undergo the following procedures as a part of their initial evaluation for chronic cough and OSA that will be done as part of their standard care.

## **CLINICAL PROCEDURES:**

We anticipate these will already be performed as part of **clinical evaluation prior to enrollment in the study (this is done as part of routine evaluation for chronic cough)**.

- Chest radiography
- Pulmonary function testing (spirometry, single breath diffusion capacity measurement)
- Exhaled nitric oxide testing if available
- STOP-BANG screening questionnaire
- Full-night attended or unattended polysomnography if STOP-BANG questionnaire abnormal with clinical suspicion for sleep-disordered breathing.

## **STUDY PROCEDURES**

- Consent Form
- Study Questionnaires:
  - Leicester-cough questionnaire (LCQ) at baseline, 6 weeks, 12 weeks and at 24 weeks
  - GERD-QoL questionnaire (GERD-QoL) at baseline and 6 weeks
  - Sino-nasal outcome test (SNOT-20) at baseline and 6 weeks
  - Asthma Life questionnaire (ALQ) at baseline and 6 weeks
- Laryngeal dysfunction scores (LDQ) at baseline and 6 weeks
- Leicester cough monitoring for 24 hours at baseline, at 6 weeks and 12 weeks.
- Exhaled breath condensate at baseline, 6 weeks and 12 weeks.
- CPAP data download at 6 weeks, 12 weeks

### **Procedures performed for research purposes only:**

Once individuals with chronic cough that meet inclusion criteria are found to have OSA on polysomnography, they will be given an option to enroll in the current study. These procedures will be done as part of the research study.

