## STUDY PROCEDURES

### 1. CONSENT FORM 2. STUDY QUESTIONNAIRES

- Leicester-cough questionnaire (LCQ) at baseline, 6 weeks, 12 weeks
- Cough VAS scale at baseline, 6 weeks and at 12 weeks
- GERD-QoL questionnaire (GERD-QoL) at baseline and at 6 weeks
- Sino-nasal outcome test (SNOT-20) at baseline and at 6 weeks
- Asthma life questionnaire at baseline and at 6 weeks
- Laryngeal dysfunction scores (LDQ) at baseline and at 6 weeks

3. Cough monitoring for 24 hours, at baseline and at 6 weeks and 12 weeks.
4. CPAP data download at 6 weeks, 12 weeks
5. Exhaled breath condensate at baseline, 6 weeks and 12 weeks.

Once patients are enrolled, they will be randomized to either straight CPAP or sham CPAP. Randomization will be done by study coordinator, [name] and treating physicians (and investigators) will be blinded to whether the patient received straight CPAP or sham CPAP. Patients will be evaluated at 6 and 12 weeks after randomization as part of study. At 6 weeks, patients will be unblinded and placed back on straight CPAP. The pressure on straight CPAP will be determined according to the results of the polysomnography or they will be kept on 10cm of CPAP (adjustments to this may be made by the study coordinator, [name] who is the CPAP coordinator for the Sleep Center). For sham CPAP, patients will be kept at 1-2cm of pressure as per sham CPAP recommendations and no adjustments to this will be made although there may be adjustments made in mask or interface used for the CPAP.

---

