## STUDY PROTOCOL

Subjects with randomized to straight CPAP (either at 10cm or at a pressure determined during PSG) OR sham CPAP (1-2cm) following mask-fitting session during PSG or prior to that. After 6 weeks of therapy, patients will evaluated for above-mentioned end-points and study analyses will be done. Patients will be then placed on CPAP (as prescribed by PSG) and followed at 12 weeks again.

**VISIT 1                    SCREENING AND ADMINISTRATION OF QUESTIONNAIRES (LCQ, GERD-QoL, SNOT-20, LDQ, ALQ; MEASUREMENT OF EBC AND COUGH MONITORING FOR 24 HOURS)**

PATIENTS WILL BE ON STRAIGHT CPAP FOR 6 WEEKS OR ON SHAM CPAP FOR 6 WEEKS.

VISIT 2 (+6wk) ADMINISTRATION OF LCQ, GERD-QoL, LDQ, SNOT-20, ALQ, SMART-CARD DATA DOWNLOAD, EBC, COUGH MONITORING FOR 24 HOURS

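### The entry criteria do not exclude patients with hazardous sleepiness, so such a patient can be randomised to six weeks of sham CPAP

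*Combined protocol and SAP*

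**What the plan says.** **Entry.** Inclusion Criteria has one sleep-related item: "STOP-BANG score of 3 or more requiring OSA evaluation". The consent section then says: "Once patients meet study criteria based on results of STOP-BANG questionnaire and polysomnography, they will be eligible to be consented by the investigators". The section on procedures performed for research purposes only offers enrolment to patients who meet the inclusion criteria and are "found to have OSA on polysomnography, they will be given an option to enroll in the current study".

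**Exclusions.** The list covers "Use of supplemental oxygen or PAP therapy", but keeps patients with earlier OSA who did not comply with PAP. It also removes users of opiates or benzodiazepines (codeine-type cough suppressants are allowed), alcoholism and drug dependence, heart failure, stroke and other major disease, and facial anatomy that prevents CPAP.

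**After enrolment.** Patients are randomised to CPAP or sham, and "treating physicians (and investigators) will be blinded to whether the patient received straight CPAP or sham CPAP". On sham pressure: "For sham CPAP, patients will be kept at 1-2cm of pressure as per sham CPAP recommendations and no adjustments to this will be made". The mask or interface may still be changed. The STUDY PROTOCOL section sets the duration: "PATIENTS WILL BE ON STRAIGHT CPAP FOR 6 WEEKS OR ON SHAM CPAP FOR 6 WEEKS". It lists Visit 1, Visit 2 at 6 weeks and Visit 3 at 12 weeks. Patients are unblinded at 6 weeks and placed on CPAP.

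**The concern.** A sham-controlled trial in OSA withholds effective treatment from half its patients for a fixed time. That is needed to answer the question, and the low, fixed sham pressure is not at issue. What matters is who may be exposed to it. For most patients with chronic cough and OSA, six weeks' delay may be acceptable. For someone who becomes sleepy while driving, or is sleepy by day and drives or runs machinery for work, the delay carries a risk of accident to that person and to others. That step is a clinical judgement; the documents do not state it.

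The criteria remove several vulnerable groups but not this one. Blinding adds to the difficulty, because a sham patient may believe that treatment has begun and the treating physician does not know otherwise. At stake is the safety of a few patients in one arm, not the validity of the cough comparison.

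**Working it through.** The main check is a reading of the criteria against the treatment schedule; the arithmetic only shows scale.

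**1. Is there an entry rule on sleepiness?**

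| Section | Sleep-related content | Excludes a hazardously sleepy patient? |
|---|---|---|
| Inclusion Criteria | STOP-BANG of 3 or more | No; it is a minimum, and a high score qualifies |
| Exclusion Criteria | Current oxygen or PAP; opiates and benzodiazepines; craniofacial abnormality | No; these concern treatment, drugs and anatomy |
| Consent process | STOP-BANG and polysomnography results | No limit on sleepiness or OSA severity |
| Research-only procedures | OSA on polysomnography | No; any OSA qualifies |

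The exclusion list is readable throughout, with only a numbering slip, so the gap does not look like removed text.

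**2. Is there a later check?** The study questionnaires are LCQ, cough VAS, GERD-QoL, SNOT-20, ALQ and LDQ. No sleepiness scale is named among them. No visit is listed between Visit 1 and week 6, and no rule for early switching or unblinding is written.

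**3. Number on sham.** The plan's own inflation for attrition reproduces: 19 / (1 - 0.33) = 28.4, rounded up to 29 per group, and 2 x 29 = 58. Maximum sham exposure is 29 x 6 = 174 patient-weeks. That covers all sham patients and says nothing about the sleepy subgroup.

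**4. Hazardously sleepy patients on sham.** The documents give no share, so p is assumed. Expected number = 29p. Chance of at least one = 1 - (1 - p)^29.

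**5. Recruitment cost of excluding them.** Otherwise eligible patients needed = 58 / (1 - p), rounded up.

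| Assumed p | 29p | Chance of at least one | 58 / (1 - p) | Needed | Extra |
|---|---|---|---|---|---|
| 2% | 0.58 | 44% | 59.2 | 60 | 2 |
| 5% | 1.45 | 77% | 61.05 | 62 | 4 |
| 10% | 2.90 | 95% | 64.4 | 65 | 7 |

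The exposure columns suppose that no clinician holds such a patient back informally.

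**The case against.** The strongest reply is that clinical process already covers much of this. Enrolment is optional, the polysomnography result is known before consent, and the investigators take consent. A clinician can decline to enrol a very sleepy patient. This stands as mitigation, but it is unwritten discretion and may vary among the pulmonary, ENT, primary care and sleep clinics that recruit. Consent pages were removed from the text under review and may carry driving advice; such advice could reduce the consequence but would not be an entry rule.

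Four stronger readings are tempting, and the documents do not support them.

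- **A reader might infer that nobody can act before week 6.** The coordinator who randomises is also the Sleep Center's CPAP coordinator and may change the mask or interface. Contact with someone who knows the allocation is therefore foreseen. What is missing is a written rule telling that person to check sleepiness or to switch a patient early.
- **A reader might infer that the protocol itself calls the delay unsafe**, from "OSA is an important clinical problem that needs to be treated for impact on cardiovascular, metabolic and behavioral outcomes". That sentence explains why OSA screening is routine care. It mentions neither driving nor a six-week delay.
- **A reader might infer that patients already on PAP are moved to sham.** Current PAP users are excluded.
- **A reader might conclude that everyone who drives or operates machinery for work should be excluded.** No hazard is shown for alert patients in such jobs. If a blanket rule removed 20% (assumed), 58 / 0.80 = 72.5, so 73 otherwise eligible patients would be needed, 15 more than 58, and the results would not apply to people in those jobs.

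It is also fair that the affected share is unknown. The size of the problem is a range of assumptions, not an estimate.

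**Conclusion.** The point holds in a limited form. The visible criteria contain no rule on hazardous sleepiness, and the plan followed as written can place such a patient on 1-2 cm sham for six weeks with physicians and investigators blinded. Under assumed shares of 2% to 10%, between 0.6 and 2.9 of the 29 sham patients would be affected.

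The absence of a rule rests on the text alone. The number affected rests wholly on the assumed shares, and the view that these patients are poor candidates for delay rests on clinical judgement. Nothing here shows that harm would occur, that sham control is inappropriate, or that the efficacy analysis is flawed. It is a cheap improvement to patient safety.

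**What to change.** Add one item to Exclusion Criteria: patients who report sleepiness while driving, or who report daytime sleepiness and drive or operate machinery for work. Do not exclude alert patients on occupation alone.

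Confirm the item at the eligibility check, before the Visit 1 breath condensate and cough monitoring and before randomisation. Because consent follows eligibility in this protocol, the amendment should say whether the questions belong to the routine clinical evaluation or are asked immediately after consent.

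The rule acts before allocation and applies to both arms, so it cannot bias the comparison between them. Sham pressure, visits, endpoints and the target of 58 stay as they are.

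The cost is a few screening questions and some loss of eligible patients, of a size the documents do not give: 2 to 7 more otherwise eligible patients under the assumed 2% to 10%. The results would not apply to patients with hazardous sleepiness. The change does not supply a rule for switching a patient who becomes sleepy during the six weeks; that is a separate gap.
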